5.6 Calculated Variables

- OS = 1 + date of death of any cause or censoring \square date of randomization (calculated in days then converted to months)
- PFS = 1 + date of PFS event or censoring \square date of randomization (calculated in days then converted to months)
- DOR = 1 + date of first documented PFS event or censoring \square date of initial documented response (CR or PR) (calculated in days then converted to months)
- For patients with no death date at the time of analysis, the Last alive date is defined as later of last non-missing eCRF dates
- Baseline is defined as the last non-missing assessment done before start of treatment
- Body Surface Area (m²) = ([height (cm) x weight (kg)] / 3600)^{0.5}
- Months = Days / 30.4375.

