5.7 Missing Data

For the primary and key secondary efficacy analyses, imputation will be performed. Imputation rules for partial PFS dates are as follows:

- 1) If year is missing, no imputation should be done;
- 2) If only day is missing, then impute the day as the 15th of the month;
- 3) If both day and month are missing, then impute the day and month as 1st of July;
- 4) All imputed dates have to be prior to the dates of withdrawal of consent, lost to follow-up, and death.

Imputation rules for partial death dates are as follows:

- 1) When only date portion is missing and month and year are available, the death date will be imputed to the last day of that month.
- 2) When date and month portion is missing and year is available, the death date will be imputed to maximum of (30th June of year of death / last known alive date / last follow up date / maximum date from selected SDTM datasets / end of study date).

For determination of treatment emergent adverse events the following rules will be applied for all treated subjects in case of missing start date:

- If end date is before the date of first treatment administration, the start date will remain missing
- If start date is missing and end date is after or on the date of first treatment administration or the end date is missing, the start date will be imputed by the date of first treatment administration
- If start date is incomplete and end date is after or on the date of first treatment administration or the end date is missing, the start date will be imputed as follows: if the day is missing then the start date will be imputed with the first day of the month; if the day and month are missing then the start date will be imputed with minimum of (1 December of the year and the AE end date).

Confidential

6. Techniques for the Analyses

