6.2 Primary Objectives

6.2.1 / □

The OS endpoint is the time from the date of randomization until death due to any cause (i.e. date of death or censoring □ date of randomization + 1). Any subject not known to have died at the time of analysis will be censored based on the last recorded date on which the patient was known to be alive. All durations will be converted from days to months for reporting purposes. The ITT population will be used.

To assess for OS differences between treatment arms, the Cox PH model will be used, specifying the Efron method for ties. This will be done using `PROC PHREG` in SAS, in which performance status and tumor location will be added in a separate `strata` statement.

Confidential

The significance of the asymptotically estimated statistics will be determined using a re-randomization procedure. The hazard ratio, p-value and confidence limits from the asymptotic test, plus the re-randomization p-value, will be reported.

The Kaplan-Meier estimator, and their respective confidence limits and p-values, will all be displayed in a table. To confirm proportionality of the hazards, the log-log survival plot should be inspected, using PROC LIFETEST and, at a minimum, specifying treatment arm in the strata statement (the stratification variables may also be included); these plots will not be included in the set of outputs.

Supplementing this test will be a Kaplan-Meier plot showing time to death from randomization, in months, by treatment arm. Underneath the plot should be a table displaying the number at risk by treatment arm at 0.5-month intervals. The plot should contain an inset with the hazard ratio, the corresponding confidence limits and p-values (both asymptotic and re-randomization test p-values).

Refer to the table below for a description of the primary and sensitivity analyses that will be performed.

No.	Stratified	Re-Randomized	Endpoint Review	Population
1. Primary	Yes	Yes	Not applicable	ITT
1. Sensitivity	Yes	No	Not applicable	ITT
2. Sensitivity	Yes	Yes	Not applicable	PP
3. Sensitivity	Yes	No	Not applicable	PP
4. Sensitivity	No	Yes	Not applicable	ITT
5. Sensitivity	No	No	Not applicable	ITT

The estimand corresponding to this primary endpoint is defined by the following 5 attributes:

TREATMENT

Combination CPI-613 + mFFX compared to standard of care FFX

POPULATION

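### SAP 5.7 sets no upper limit on the imputed date of a death known only by year, so an OS event can be dated after the year in which the patient died

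*SAP*

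**What the plan says.** SAP 5.7 has two rules for partial death dates.

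- Day missing: "the death date will be imputed to the last day of that month".
- Day and month missing: "the death date will be imputed to maximum of (30th June of year of death / last known alive date", and the list continues "last follow up date / maximum date from selected SDTM datasets / end of study date".

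The second rule has no upper bound. The selected datasets are not named. The SAP does not say whether the end-of-study date belongs to the patient or to the trial.

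The same section does bound imputed progression dates: "All imputed dates have to be prior to the dates of withdrawal of consent, lost to follow-up, and death". Death dates get no comparable limit.

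SAP 5.6 turns these dates directly into the endpoint ("OS = 1 + date of death of any cause or censoring", minus the randomization date). For patients with no death date it says "Last alive date is defined as later of last non-missing eCRF dates". SAP 6.2.1 says such patients are "censored based on the last recorded date on which the patient was known to be alive".

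**The concern.** A maximum that includes the last known alive date is a sensible floor, because nobody can die before being seen alive. The other terms are not evidence of life. A follow-up form, a dataset record or a study-end date can all be later than the death. Without a cap, the rule can replace a known fact (the year of death) with a date that contradicts it.

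The endpoint is OS, so each extra day lengthens a primary event time by one day. The five OS sensitivity analyses in SAP 6.2.1 vary stratification, re-randomization and population. None varies date handling, so all of them carry the same dates. There may also be a knock-on for PFS. Under SAP 6.3.1 a death after a gap of 126 days without scans is censored at the last evaluable scan, so a death moved late could stop counting as a PFS event.

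**Working it through.** **Design figure.** Inputs from SAP 3.3: HR 0.7, one-sided 0.025, power 90%; 1:1 allocation from SAP 3.2. (1.960 + 1.282)² = 10.51.

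- Schoenfeld: 4 × 10.51 / (ln 0.7)² gives 331 deaths.
- Freedman: 10.51 × (1.7/0.3)² gives 338 deaths.

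The planned 335 lies between them, with power 0.904 by Schoenfeld. The date rule does not alter this figure.

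**One patient (assumed dates).** Randomized 1 March 2019, death known only as 2019. OS in months = (1 + days)/30.4375, from SAP 5.6.

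| Date that decides the maximum | Days + 1 | OS (months) |
|---|---|---|
| 30 June 2019 | 122 | 4.01 |
| 31 December 2019 (latest possible) | 306 | 10.05 |
| Patient-level form, 15 February 2020 | 352 | 11.56 |
| Trial-level end, 31 August 2021 | 915 | 30.06 |

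The last two rows cannot be true for a 2019 death, and the rule as written produces both.

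**Simulation.** 1,500 trials per scenario, 528 patients (SAP 5.1.1), exponential OS with medians 12 and 17.14 months, uniform accrual over 33 months, cut at the 335th death, unstratified log-rank and Cox. Assumed, not in the documents: the share of year-only deaths, accrual starting 10 months into a calendar year, and a trial-level end date equal to the cut. The patient-level reading uses the next 2-monthly contact after death.

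Among year-only deaths at HR 0.7:

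- Trial-level: 90% to 91% fall after the known year, mean shift 15.4 to 15.8 months.
- Patient-level: 9% to 10%, mean shift about 2.0 months.
- Capped at the earlier of 31 December and the cut: none, mean shift 0.82 to 0.87 months.

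At HR 1.0 the figures are 62% to 63% and about 14 months (trial-level), and 7% to 8% and about 2.0 months (patient-level). The trial-level share depends on where the cut falls in the calendar year. On average it falls at 39.4 + 10 = 49.4 months, 1.4 months into a new year, under HR 0.7. Under HR 1.0 it falls at 36.4 + 10 = 46.4, still inside the fourth year.

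Equal shares in both arms, HR 0.7:

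| Share | Reading | HR | Power | Medians, experimental / control |
|---|---|---|---|---|
| 0% | none imputed | 0.702 | 0.903 | 17.14 / 12.04 |
| 2% | trial-level | 0.702 | 0.896 | 17.57 / 12.36 |
| 5% | trial-level | 0.706 | 0.886 | 18.19 / 12.86 |
| 10% | trial-level | 0.715 | 0.868 | 19.06 / 13.70 |
| 5% | patient-level | 0.699 | 0.900 | 17.30 / 12.13 |
| 10% | patient-level | 0.700 | 0.887 | 17.35 / 12.22 |
| 5% | capped | 0.698 | 0.901 | 17.25 / 12.06 |

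Monte Carlo error on power is about 0.8 points.

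**The case against.** **The large delays need a strained reading.** If the end-of-study date were trial-level, it would exceed nearly every patient date and make the other four terms redundant. SAP 7.1 tabulates patients who terminated the study, so a patient-level date plausibly exists. The protocol's own trial-level term, in 5.4, is end of trial. This stands as a reason not to infer that year-only deaths will be misdated by years. It does not remove the defect, because the term is undefined and the cap is missing under either reading.

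**Such deaths should be rare.** Protocol 7.3.5 checks survival every 2 months, using hospital and death records among other sources. Protocol 8.4.2 has deaths reported within 24 hours of site awareness. This stands. The documents give no count.

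**Bias between arms.** In an open-label trial a reader might infer a biased comparison. If 5% of deaths in the experimental arm and none in the control arm were year-only, the trial-level reading gave one-sided rejection of 0.058 under the null, and 0.026 with the cap. But those unequal shares are invented, the follow-up schedule is the same in both arms, and the documents do not support an imbalance.

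**Month-end dates.** A reader might count these as an error too. They stay within the known month and are an ordinary convention.

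**Last-alive date.** A reader might see 5.6 as contradicting 6.2.1. Read together, 6.2.1 supplies the principle that 5.6 leaves out. The definition in 5.6 is loose and needs aligning. It sets the censoring date only for patients with no death date. Nothing shows that the eCRF records dates such as failed calls.

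**Conclusion.** The year-only rule is wrong as written: followed literally, it can date a primary-endpoint event after the known year of death. How often and by how much depends on an undefined term. A trial-level date misplaces most year-only deaths, often by more than a year. A patient-level date misplaces few, with a mean shift of about 2 months across all year-only deaths.

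With equal shares of 2% to 5%, the HR and power hardly move under either reading. The visible effect is on the medians, up to about 1 month at 5% under the trial-level reading (18.19 against 17.14, and 12.86 against 12.04). These sizes rest on assumed shares and calendar dates. The documents establish neither an inflated type I error nor a difference between the arms.

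**What to change.** In SAP 5.7:

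- Year only: the later of 30 June (or 1 July) of the death year and the day after the last documented contact alive, capped at the earlier of 31 December of that year and the data cut-off.
- Remove the end-of-study date and the SDTM maximum from the rule. A last follow-up date should count only if it documents the patient alive.
- Day only: keep month end, capped at the data cut-off.
- Treat a documented contact alive that is later than the cap as a data query, not as an imputation.

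In SAP 5.6, limit the last-alive date to listed eCRF dates that show the patient alive, and cross-refer to 6.2.1.

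Reporting the number of imputed death dates by arm would show whether the point mattered. The cost is a few lines of SAP text before database lock, with no new data and no change to the 335 deaths.

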6.1 Re-Randomization Tests

Patients will be allocated to either the control arm or the experimental arm using stochastic minimization, a dynamic treatment allocation procedure that produces good balance with respect to several prognostic factors between the randomized arms (Buyse, 2000). When such a procedure is used, the preferred test is a re-randomization test (Simon, 1979) based on a large number of simulated trials in which patients are re-allocated randomly to the control arm or the experimental arm using the same stochastic minimization, so as to produce an empirical distribution of the test statistic under the null hypothesis. This empirical distribution is used to assign a statistical significance, via an empirically estimated re-randomization p-value, to the observed asymptotic test statistic calculated using the original randomization allocation. Arbitrary precision on the re-randomization p-value can be obtained by increasing the number of simulated trials.

On this study, re-randomization tests will be used as the primary method of analysis, with additional asymptotic tests used as sensitivity analyses. For each analysis where re-randomization tests are used, a total of 10000 simulations will be conducted, in which the seed passed to the stochastic minimization algorithm is randomly generated. Patients will be re-randomized in the same order they were originally randomized. As the stochastic minimization proceeds within each site, the next patient to be randomized is compared on the basis of performance grade and tumor location (i.e., the stratification factors) to the patients previously randomized in that site, and the preferred treatment arm is the one that minimizes the imbalance in strata. The stochastic minimization algorithm is designed so that a patient has an 80% chance of being allocated to the preferred treatment arm, therefore subsequent re-randomizations will introduce new allocations.

This process will generate a total of 10000 treatment allocations, i.e., 10000 variations of `trt01p`. For each of these treatment allocation variants, the pre-specified statistical analysis (e.g., Cochran-Mantel-Haenszel) will be carried out, and the subsequent test statistic estimates will be recorded. The empirical p-value is the frequency, calculated as total number of times out of 10000, that a simulated test statistic is strictly larger (i.e., more extreme) than the asymptotically estimated test statistic on the observed data using the original randomization allocation. For a given analysis, the summary table will display the asymptotic parameter estimate and confidence interval, plus the empirically estimated p-value.

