3.3 Sample Size Justification

A total of 500 patients will be enrolled in this trial across approximately 100 sites in North America, Europe, Asia, and Oceania. This number accounts for ineligible and unevaluable patients, as well as for dropouts.

Dropouts refer to any subject who has been randomized but withdrew for various reasons, including misdiagnosed or exclusion criteria violations.

The sample size calculation is based on the following expected benefits of the experimental treatment (CPI-613 + mFFX) over the control treatment (FFX):

- A 30% reduction in the risk of death from any cause; specifically, median OS is assumed equal to 12 months in the control arm vs. 17.14 months in the experimental arm, i.e., an OS hazard ratio equal to 0.7. For a power of 90% and a one-sided type-I error level of 0.025, 335 deaths need to be observed.
- A 30% reduction in the risk of tumor progression or death from any cause; specifically, median PFS is assumed equal to 6.4 months in the control arm vs. 9.14 months in the experimental arm, i.e., a PFS hazard ratio equal to 0.7. For a power of 90% and a one-sided type-I error level of 0.025, 330 PFS events need to be observed.

4. Data Sources

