4.1 Randomization

Subjects will be randomized in a 1:1 ratio to the experimental treatment or control via an interactive web response system (IxRS), using a minimization procedure. The minimization algorithm will use the variance method to minimize overall imbalances between the treatment arms with respect to site, and the stratification factors: performance status (0 vs. 1); and, primary tumor location (head vs. body vs. tail of the pancreas). Note that region is subsumed by site, hence minimization will also tend to balance between the treatment arms with respect to geographical region.

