4.4 ECG

The 24 patients receiving CPI-613 plus modified FFX (i.e., Arm 1) assigned to the full PK analysis sub-study will also undergo a full ECG analysis. 12-lead ECGs will be recorded at defined intervals from 30 minutes prior to dosing of CPI-613 on cycle 1, day 1 to 6 hours after dosing on day 1. Subjects will be placed in a supine position for at least 10 minutes prior to timepoints for ECG and PK sampling. ECG recordings will be taken immediately prior to PK sample draw at each time point. ECG intervals for this full ECG analysis will be measured at a central ECG laboratory, who will be fully blinded to timepoints and subject identification.

5. General Analysis Definitions

Data will be analyzed using SAS (version 9.4 or higher).

Descriptive statistics will be tabulated as follows:

- Categorical data will be summarized in contingency tables presenting frequencies and percentages.
- Continuous data will be summarized using number of non-missing values (n), mean, standard deviation, median (25th, 75th), minimum, and maximum values.

The baseline tables will be created by treatment arm and overall. Tables containing post-randomization information will be displayed by treatment arm, unless otherwise specified.

Listings with individual values will be provided for all data presented in the tables, where noted. The listings will be presented by identifiers, such as treatment group, center, and patient number.

Confidential

One-sided tests will be used at a significance level equal to 0.025. Two-sided confidence intervals will be computed for a coverage of 0.95.

Time-to-event analyses will be performed using the Kaplan-Meier method. Subjects who have not had the event of interest at the time of the analysis will be censored at the time of the last follow up. Summary statistics will be provided by treatment arm in terms of the number of events, number of censored observations, median, and 95% confidence interval, and survival probabilities at specific time points (such as 1 year, 2 years, etc.). Survival curves will be plotted by treatment arm and compared with a log-rank test stratified by performance status and tumor location. A stratified Cox regression model will be used to estimate the hazard ratio and its 95% CI, as well as to adjust the comparison for baseline covariates.

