5.4 Control Of Type I Error

This study has one primary endpoint of OS. The key secondary efficacy endpoint is PFS.

Testing of these two endpoints will proceed as follows in order to control the overall one-sided type I error of 0.025:

- OS will be tested at a significance level of 0.025. OS will be tested only once at the final analysis.
- PFS will be tested conditionally on the primary endpoint of OS reaching statistical significance, using the significance level of 0.025.
- If OS reaches statistical significance and PFS also reaches statistical significance, then the hierarchical testing procedure will continue to test the rest of the other secondary endpoints in the following order: ORR first, and then DOR, each at a significance level of 0.025.

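### The deciding OS p-value rests on 10,000 re-randomisations with no stated master seed or borderline rule, so a result very close to 0.025 can depend on the seed; the overall effect is small and the fix is cheap.

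*SAP*

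**What the plan says.** Protocol 9.4.3 and SAP 6.1 give the re-randomisation test the deciding role. In the SAP's words, "re-randomization tests will be used as the primary method of analysis, with additional asymptotic tests used as sensitivity analyses". For each such analysis, "a total of 10000 simulations will be conducted, in which the seed passed to the stochastic minimization algorithm is randomly generated". The p-value follows directly from the draws: "The empirical p-value is the frequency, calculated as total number of times out of 10000" on which a simulated statistic exceeds the observed one.

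SAP 5.4 sets the threshold and the number of looks: "OS will be tested at a significance level of 0.025. OS will be tested only once at the final analysis". PFS is tested only if OS passes, then ORR, then DOR, each at 0.025.

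Both documents note that precision can be raised at will by adding simulated trials. Neither sets a precision target. The text available gives no master seed, no duty to archive seeds, no Monte Carlo interval, and no rule for a result close to 0.025. SAP 6.2.1 reports the asymptotic p-value beside the re-randomisation p-value but gives it no tie-breaking role.

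**The concern.** A re-randomisation p-value computed from a finite number of draws is an estimate with its own sampling error, separate from the uncertainty in the trial data. If the exact value lies close to 0.025, two runs on identical data can fall on opposite sides of the threshold. The OS claim, and the opening of the hierarchy for PFS, ORR and DOR, would then rest on the random number stream.

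Protocol 9.4.3 leaves the full details of the re-randomisation tests to the SAP, so SAP 6.1 is where the seed and the precision should be settled. A borderline result found after unblinding would be hard to repair credibly.

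**Working it through.** **Inputs**
- One-sided level: "One-sided tests will be used at a significance level equal to 0.025" (SAP 5, General Analysis Definitions).
- Design effect: "an OS hazard ratio equal to 0.7" (SAP 3.3).
- Events: "For a power of 90% and a one-sided type-I error level of 0.025, 335 deaths need to be observed" (SAP 3.3).
- Allocation: 1:1 (SAP 4.1).
- Draws: B = 10,000 (SAP 6.1).
- Hazard ratio 0.8: my assumption, to show a weaker effect. It is not in the documents.

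**Step 1. The plan's own figure.** Schoenfeld: 4(1.960 + 1.282)² / (ln 0.7)² = 331 deaths. Freedman's formula gives 338. The plan's 335 lies between them and gives 90.4% power, so it is reproduced.

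**Step 2. Monte Carlo error at the threshold.** SE = √(p(1 − p)/B) = √(0.025 × 0.975 / 10,000) = 0.00156. The 95% range is 0.025 ± 1.96 × 0.00156 = 0.0219 to 0.0281.

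**Step 3. Chance that one run is positive.** The count is Binomial(10,000, p), where p is the exact re-randomisation p-value. A run is positive if the count is at most 250.

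| Exact p | One run positive, B = 10,000 |
|---|---|
| 0.022 | 98.0% |
| 0.023 | 91.3% |
| 0.024 | 75.5% |
| 0.025 | 51.7% |
| 0.026 | 27.7% |
| 0.027 | 11.4% |
| 0.028 | 3.5% |

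The SAP does not say whether a p-value of exactly 0.025 counts as significant. Under a strict inequality the figures at 0.024 and 0.026 are 73.5% and 25.7%.

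The chance of a positive run lies between 2.5% and 97.5% for exact p from 0.0221 to 0.0283. With 335 deaths, HR = exp(−2z/√335) turns this into an observed hazard ratio of about 0.803 to 0.812. The critical value is about 0.807.

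**Step 4. How often this changes the verdict.** Take the log-rank Z as normal with variance 1 and mean (√335/2) × ln(1/HR), which is 0, 3.26 and 2.04 at HR 1, 0.7 and 0.8. Let p = 1 − Φ(Z) stand in for the exact re-randomisation p, and let q(p) be the chance of a positive run from Step 3. A single run errs with chance 1 − q if p ≤ 0.025, and q otherwise. Averaging over Z gives:

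| True HR | Wrong verdict, B = 10,000 | Wrong verdict, B = 100,000 | Chance of a positive trial: exact p / 10,000 draws |
|---|---|---|---|
| 1 (null) | 0.12% | 0.04% | 2.50% / 2.51% |
| 0.7 | 0.36% | 0.11% | 90.4% / 90.4% |
| 0.8 (assumed) | 0.85% | 0.27% | 53.3% / 53.3% |

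**Step 5. What more draws buy.** At B = 100,000 the 95% half-width at p = 0.025 is 1.96 × √(0.025 × 0.975 / 100,000) = 0.00097, against 0.0031 now. The unstable band narrows to 0.0241–0.0260. An exact p of 0.024 is then called positive 98% of the time. A half-width of 0.001 needs 1.96² × 0.025 × 0.975 / 0.001², or about 94,000 draws.

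**Step 6. The p-value formula.** Replacing b/B by (b + 1)/(B + 1) at b = 250 gives 251/10,001 = 0.0250975, a change of less than 0.0001.

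**The case against.** The strongest reply is that this hardly ever matters. The plan calls for one run per analysis, and that run differs from the exact verdict in well under 1% of trials in every scenario tried. Errors fall in both directions and almost cancel, so type I error and power do not move. All of this stands, and it limits the weight of the point.

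Three stronger readings are tempting, and the documents do not support them.

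- **That the p-value cannot be reproduced.** Each replicate needs its own seed to give a new allocation, so randomly generated replicate seeds are compatible with an archived master seed. A seed rule in a programming specification, or in SAP text not available here, cannot be excluded. What can be said is that the SAP text does not state one.
- **That the plan leaves room for a rerun after a near miss.** SAP 6.1 fixes the total at 10,000 for each analysis and SAP 5.4 has OS tested once. Nothing provides for a second run, and one would depart from the SAP.
- **That counting b out of 10,000 makes the test materially invalid.** Step 6 shows a shift of less than 0.0001, and an estimate of zero could not change a verdict at 0.025.

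Reporting the asymptotic p-value alongside would make a discordant borderline result visible. It would not settle it, because the SAP ranks that test as a sensitivity analysis.

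The reply does not remove the gap itself. The SAP acknowledges that precision is available for the asking, then fixes 10,000 without justifying it and is silent on the seed and on borderline results.

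**Conclusion.** The point holds as an inexpensive improvement to the SAP. It is not a flaw in the design or in error control. If the exact re-randomisation p lies between roughly 0.022 and 0.028, the verdict on OS can depend on the seed. At an exact p of 0.024, about one run in four would be called non-significant. Over all outcomes, one run gives a different verdict from the exact p in about 0.1% of trials under the null, 0.4% at the design hazard ratio and 0.8% at an assumed 0.8.

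These figures rest on independent draws, on the normal approximation standing in for the exact re-randomisation p, on 335 deaths at analysis, and on p ≤ 0.025 counting as significant. They were computed for OS. The standard error at the threshold is the same for PFS, ORR and DOR because it depends only on p and B.

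**What to change.** Amend SAP 6.1 before database lock:

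1. Name one master seed, derive all replicate seeds from it, and archive it with the program. This makes the reported value repeatable but does not reduce its error.
2. Raise the number of re-randomisations to at least 100,000 for the primary OS test and for the PFS, ORR and DOR tests. Alternatively, keep 10,000 and pre-specify an extension to a stated larger number if the Monte Carlo interval covers 0.025.
3. Optionally, report (b + 1)/(B + 1) with its Monte Carlo interval.

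One million draws would be more than is needed. The cost is a few SAP sentences and computing time, with no change to data or design. If each replicate (minimisation plus stratified Cox fit) takes 0.1 to 1 second, which is an assumption, 100,000 replicates take 10,000 to 100,000 seconds, or about 3 to 28 hours of serial computing per analysis.
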